1.1: Nicotine deprived smokers will display selectively increased negative affect measured via startle potentiation during uncertain (vs. certain) threat relative to non-deprived smokers.

AIM 2: Examine the impact of stress neuroadaptation on negative affect, smoking urge, and smoking in response to stressors. Laboratory startle potentiation measures of stress neuroadaptation will predict ecological momentary assessment measures of:

2.1 ...overall levels of negative affect and urge
2.2 ...within-smoker covariation (i.e., coupling) of episodic stressors with negative affect, urge, and smoking (i.e., stressor-induced negative affect, urge and smoking).

AIM 3: Examine the impact of this stress neuroadaptation on smoking during the first two weeks of smoking cessation.

3.1: Laboratory startle potentiation measures of stress neuroadaptation will predict overall smoking during the first two weeks post-quit as well as measures of point prevalence abstinence and continuous abstinence measured at 2 weeks post-quit.

AIM 4: Determine if treatment of withdrawal via NRT reduces the influence of stress neuroadaptation.

4.1: Combo NRT with counseling (vs. placebo NRT with counseling) will reduce startle potentiation measures obtained at one week post-quit.

4.2: The effect of combo NRT (vs. placebo NRT with counseling) on smoking and related outcome measures will be mediated by change in startle potentiation measures from pre-quit to post-quit.

4.3: Treatment of withdrawal symptoms via combo NRT will attenuate the predictive strength of pre-quit startle potentiation measures with respect to overall levels of negative affect, urge, and smoking and stressor-induced negative affect, urge, and smoking.

RESEARCH DESIGN AND METHODS

C1: BRIEF OVERVIEW

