Additional covariates will be considered for each GLM to reduce error variance and increase power (e.g., resting startle response, task order, block order). All experiments include equal numbers of men and women to allow for preliminary examination of possible sex effects. Trait individual difference variables (e.g., individual differences in anxiety, depression, levels of tobacco dependence; see section C2.2) can be included in the GLMs to provide exploratory tests for potentially interesting moderators. Quantitatively measured withdrawal symptoms (WSWS) and smoking urge (QSU) can be included in supplemental analysis to clearly link deprivation status effects on startle potentiation to these proximal processes. Given that all participants complete both threat tasks, follow-up GLMs can include task as a within-subject factor to determine if effects are consistent across tasks that involve different manipulations of anxiety (i.e., low probability vs. temporally uncertain threat). This will provide important construct validation and potential conceptual replication of possible anxiety findings.

Analysis of Ecological Momentary Assessments of Stressors, Affect, Urge and Smoking (AIMS 2, and 4.3)

Analysis of EMA data will follow directly from procedures described by our Co-I, [name], in McCarthy, Piasecki, Fiore, & [name] (2006). Although the focal questions in McCarthy et al (2006) were different, the nature of that dataset was very similar in that it included multiple weeks of 4X daily EMA reports of stressors,

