affect, cigarette use, and withdrawal symptoms. The within-subjects, repeated measures design associated with EMA survey make it suitable for **growth-curve modeling**, a technique that estimates change over time via **multilevel modeling** (147,148). Although time is not a focal factor in our analysis, growth curve modeling is well-suited for these data and our questions because it can easily accommodate missing data and unequal intervals between assessments that result from pseudo-randomly selecting assessment times during each day. This multilevel model allows us to predict “occasion-level” (level 1) responding associated with affective response, urge, or smoking with other occasion-level variables (e.g., stressor occurrence), or “person-level” (level 2) variables (e.g., startle potentiation measures from cued threat task). Therefore, these models will provide clear and powerful tests to determine if laboratory startle potentiation “biomarkers” of stress neuroadaptations predict individual differences in overall levels of negative affect, urge, or smoking over the 3-weeks of EMA controlling for stressor exposure (AIM 2.1). Furthermore, these same models will provide tests if startle potentiation measures of stress neuroadaptation predicts individual differences in the size of the occasion-level stressor effects on negative affect, urge and smoking (i.e., stress-induced negative affect, urge, and smoking). In other words, do our laboratory stress neuroadaptation measures predict stressor-affect, stressor-urge, and stressor-smoking covariation or coupling over time (AIM 2.2). Treatment condition can be included as a moderating between-subject factor to test if the relationship between startle potentiation and overall levels and coupling of EMA measured affect, urge and smoking differ generally when withdrawal symptoms are treated via combo NRT (AIM 4.3). As with GLM analyses, these multilevel models can accommodate other exploratory person-level moderators of these effects (e.g., trait anxiety, depression, level of dependence, sex). As before, the models can also include task as a factor to determine if anxiety as measured in the laboratory task displays comparable relationships with occasion-level EMA data

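### Aim 2.1 claims control for stressor exposure, but the only stressor term named is occasion-level, which in general leaves between-smoker exposure differences partly or wholly uncontrolled

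*Combined protocol and SAP*

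**What the plan says.** The relevant text is under Statistical Considerations, in the section on analysis of the ecological momentary assessments (Aims 2 and 4.3).

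- **Aim 2.1.** The models test whether startle measures "predict individual differences in overall levels of negative affect, urge, or smoking over the 3-weeks of EMA controlling for stressor exposure (AIM 2.1".
- **Stressor term.** Occasion-level responses are predicted "with other occasion-level variables (e.g., stressor occurrence". Nothing says whether this variable is raw, grand-mean centred or person-mean centred.
- **Person-level terms.** The example is "variables (e.g., startle potentiation measures from cued threat task". Further terms are optional: "these multilevel models can accommodate other exploratory person-level moderators of these effects (e.g., trait anxiety, depression, level of dependence, sex". A smoker's average stressor exposure is not among them.
- **Aim 2.2.** For coupling, "these same models will provide tests if startle potentiation measures of stress neuroadaptation predicts individual differences in the size of the occasion-level stressor effects".
- **Source of detail.** "Analysis of EMA data will follow directly from procedures described by our Co-I", in a cited diary study that the document does not reproduce. The opening of Statistical Considerations describes what follows as a sketch of exemplars.

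C2.5.1 accepts that stressor reports are subjective and depend on each participant's own appraisal.

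**The concern.** Aim 2.1 compares smokers with one another: do those with larger startle potentiation have higher affect, urge or smoking overall? To adjust that comparison for stressor exposure, the model must account for the fact that some smokers report more stressors than others. An occasion-level indicator mainly carries a different contrast, between a smoker's stressor and non-stressor occasions.

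Smokers who report many stressors may have higher affect by more than the within-smoker slope implies. The excess (the contextual effect) then stays in the person intercept. If startle is correlated with reported stressor rate, startle picks that excess up. Aim 2.1 could then credit the laboratory biomarker with predicting overall negative affect, after supposed control for exposure, when it only tracks how often a smoker reports stressors. The intercept part of Aim 4.3 rests on the same model.

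**Working it through.** **The plan's own figure.** The document states no error rate for the Aim 2.1 test, so there is none to reproduce. The sample-size figure in C4.3 concerns a different test.

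**Inputs from the document.** There are 300 smokers, 150 per treatment group (C4.3). Reports are made 4 times a day for 3 weeks (C2.5), so 4 × 21 = 84 at most. At the 80% response rate cited there, 0.80 × 84 ≈ 67 per smoker.

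**Assumptions, not in the document.** The outcome is continuous and the stressor is yes/no. Mean stressor rate is about 0.28, with SD between smokers 0.146 (about 0.15). The within-smoker slope is 0.4, person-intercept SD 0.6 and residual SD 0.8. The true startle effect is zero and the test is two-sided at 5%. Two quantities are varied: the correlation ρ of standardised startle with exposure propensity, and the contextual effect c (between-smoker slope minus within-smoker slope).

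**Step 1: what each coding leaves in the startle coefficient.**

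- Raw entry: with this many reports the fitted slope is essentially the within-smoker slope. In simulation it stayed at 0.40 to 0.41 even when the between-smoker slope was 0.4 + 2 = 2.4. Bias ≈ c × ρ × 0.146.
- Grand-mean centring: the same model, shifted by a constant.
- Person-mean centring alone: bias ≈ (0.4 + c) × ρ × 0.146. A bias remains even when c = 0.
- With the person mean at level 2: bias is close to zero.

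**Step 2: hand check for raw entry.** The standard error is approximately √{[c² × 0.146² × (1 − ρ²) + 0.6² + 0.8²/67] / 300}.

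- ρ = 0.2, c = 1: bias 0.029, SE √(0.390/300) = 0.036, ratio 0.81, rejection about 13%.
- ρ = 0.3, c = 1: bias 0.044, SE √(0.389/300) = 0.036, ratio 1.22, about 23%.
- ρ = 0.3, c = 2: bias 0.088, SE √(0.447/300) = 0.039, ratio 2.27, about 62%.

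These run slightly high because the simulation applies ρ on the logit scale of the stressor rate.

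**Step 3: simulation.** Random-intercept model, 4,000 replicates per row; entries are rejection rates for startle.

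| ρ | c | Raw | Person-mean centred only | With person mean |
|---|---|---|---|---|
| 0.2 | 1 | 0.119 | 0.190 | 0.048 |
| 0.3 | 1 | 0.223 | 0.374 | 0.049 |
| 0.2 | 2 | 0.310 | 0.390 | 0.055 |
| 0.3 | 2 | 0.594 | 0.727 | 0.064 |
| 0.2 | −1 | 0.118 | 0.071 | 0.052 |

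A separate simulation at c = 1 and ρ = 0.2 to 0.3 gave 13% to 24% raw, 20% to 39% centred only, and about 6% with the person mean. With 150 smokers, ρ = 0.3 and c = 1, rejection was 0.153 raw against 0.056 with the mean (1,000 replicates).

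**Step 4: when raw entry is adequate.** With c = 0, raw rejection was 0.045 to 0.067 for ρ from 0 to 0.3. With ρ = 0 it was 0.040 to 0.057. Both conditions are needed for inflation.

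**Scale of c.** Values of 1 and 2 correspond to correlations of about 0.24 and 0.44 between exposure and the unexplained person intercept.

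**The case against.** The strongest reply is that the plan sketches options, gives its variable lists as examples, and defers detail to a cited procedure. On that view this is an unstated choice, not an error. Part of this stands. A reader might infer that the plan enters the stressor raw, but the document does not say so. The gap does not depend on that inference, because none of the three usual codings supplies full between-smoker control without a person-level exposure term, and none is named.

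A reader might also infer that exposure goes entirely uncontrolled. That is too strong: raw entry adjusts at the within-smoker slope and suffices when the two slopes are equal. Nor are the rejection rates estimates for this trial, since the document gives neither ρ nor c.

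A third stronger reading is that Aim 2.2, on "within-smoker covariation (i.e., coupling) of episodic stressors with negative affect, urge, and smoking", is also damaged. The calculations do not support it: a simulated coupling test rejected in 4% to 6% of trials under either specification.

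Finally, C2.5.1 ties stressor reports to individual appraisal and treats such differences as central to the predictions. Reported exposure may therefore lie on the pathway from startle to affect, and conditioning on its mean could remove part of a real effect. This stands. It is a reason to report both estimates, but the plan's stated test is the one controlling for exposure.

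**Conclusion.** The concern holds in a limited form. The plan promises control for stressor exposure in a between-smoker test and names only an occasion-level stressor with unstated centring, which does not in general deliver that control in full.

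If startle correlates with reported stressor rate and the between- and within-smoker slopes differ, raw entry makes the test reject too often. Under the assumptions above this runs from about 5% with either condition absent, through 12% to 24%, to about 60% in the most extreme setting. With the person mean it is 5% to 6%. A negative contextual effect biases startle downward instead. Person-mean centring alone was worse than raw entry in every positive-effect setting tried.

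Limits: cigarette counts were not simulated. A random stressor slope was checked only in one small run with no contextual effect (200 replicates: 0.03 raw, 0.04 with the mean). The size of any effect on Aim 4.3 was not computed.

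**What to change.** State the model for Aim 2.1 explicitly:

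- Person-mean centre the occasion-level stressor.
- Add each smoker's mean stressor exposure, grand-mean centred, at level 2.
- Test Aim 2.1, and the intercept moderation in Aim 4.3, on startle in that model.
- If a product of mean exposure and startle is included, build it from the grand-mean-centred mean, so that the startle coefficient applies to a smoker with average exposure. With an uncentred mean it would apply to a smoker with no stressors, and its standard error would rise by about √[1 + (0.28/0.15)²] ≈ 2.1 times.
- Also report the startle effect without the person mean, because reported exposure may be on the pathway.

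The cost is one level-2 term and one further reported estimate per model. No new data are needed, since the person mean comes from reports already collected. The small downside is that two startle estimates must be interpreted together; the plan should say in advance that the adjusted one is the Aim 2.1 test.

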All participants report some demographic information, their current affective state (Positive and Negative Affect Scales-PANAS (120), provide information on a broad-band personality measure (Brief Multidimensional Personality Questionnaire- bMPQ); (121) and supplemental measures of trait affectivity relevant to individual differences in anxiety including the Intolerance of Uncertainty Inventory, (122), and the Anxiety Sensitivity Inventory (123). Individual differences in depressive symptoms will also be recorded Center for Epidemiologic Studies Depression Scale Revised (CESD-R; 125) and the Depression Anxiety Stress Scale-21 (DASS-21).

These measures are available to serve as covariates to increase power to test for focal effects on relevant outcome measures. They are also available as possible individual difference moderators in supplemental analyses. After completing the self-report measures, participants schedule their first experimental session. Participants are randomized to either a nicotine deprived or non-deprived condition and instructed to abstain from all nicotine containing products for 24 hours prior to their nicotine deprived session or to continue their normal pattern of smoking prior to their non-deprived session.

Finally, participants receive brief cessation counselling, schedule their experimental visits and quit date, and are provided with verbal and written instructions about the 3-week daily EMA survey that begins one week before their quit date.

C2.3: Laboratory Experimental Session(s)

All participants complete the cued threat task (NPU; see section C3 below) in each of two separate experimental sessions. Their first session is either nicotine deprived and non-deprived in a counterbalanced order, the final is 2 weeks post-quit. The deprived group completes their first experimental session the day after the start of their quit attempt, and the non-deprived group completes it before the start of their quit attempt. Data across the two experimental sessions will be used to provide sensitive within-subjects tests of deprivation effects on startle potentiation measures of stress neuroadaptation (Aim 1) and to address all subsequent Aims (2-4).

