On arrival at the laboratory for each of both experimental sessions, participants report the time of their last cigarette and have their CO level measured. For the nicotine deprived session, participants must self-report no tobacco use within the last 24 hours and have a CO level < 6ppm. If they fail to abstain from tobacco products, they are rescheduled once. Our experience across many previous nicotine deprivation studies (33,58,86,126,127) with similar monetary incentives suggest fewer than 5% of participants will fail to abstain for their first scheduled deprivation session and require rescheduling. The majority of these participants will succeed in their second attempt. If they fail to abstain a second time, their participation is discontinued. These estimates are likely conservative given that the current sample is motivated to quit. As such, we do not expect attrition due to failure to abstain to bias the sample substantially. Following this, all participants complete a measure of their current affective state (PANAS), smoking urge (QSU) and withdrawal (WSWS) described earlier.

On completion of the task, participants receive brief cessation counseling, and combo NRT or placebo NRT according to their randomized treatment condition (see below).

C2.4 Treatment Groups

Participants are **randomly** assigned to one of two treatment groups: combination NRT (patch and lozenge) vs placebo NRT, both accompanying by motivational enhancement counseling. Due to the different visit calendars required for the two arms, study staff are not blinded to treatment arm.

Combination NRT: Participants assigned to the combo NRT arm will use 21-mg nicotine patches for 2 weeks. Participants will be given instructions on how to use the patch consistent with recommended use (20). They will be told to apply one patch each morning to a non-hairy body surface between the neck and waist. Moreover, they will be encouraged to report any side effects promptly so that steps may be taken to facilitate effective medication use (e.g., use of cortisone cream for skin reactions). Participants will also be provided with nicotine lozenges (2-mg). Participants will be instructed on recommended lozenge use (20). They will be encouraged to use at least one piece every 1-2 hours and to establish a consistent schedule to prevent rather than ameliorate craving and/or withdrawal symptoms. Both NRT patches and lozenges are over-the-counter “Up and Up” brand (purchased through Target.com).

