our and other laboratories, shock intensity during these tasks is calibrated to each participant's individual sensitivity threshold, which is assessed prior to the main task during each experimental session to reduce individual differences (34,62,64,135). Startle potentiation is the primary dependent measure of affective response. As reviewed earlier, basic affective neuroscience research has indicated that startle potentiation is a sensitive and selective index of the neurobiological substrates of fear and anxiety, respectively, during conditions of certain vs. uncertain threat (30,72,74).

Participants in the non-deprived group will complete the task once pre-quit; in the deprived group, immediately post-quit, while both groups will also complete the task 2 weeks post-quit (counterbalanced) in separate experimental sessions separated by approximately two weeks. Task details are provided below. Task order within an experimental session is counterbalanced across all participants. We have preliminary data among 23 smokers in the context of an ongoing study that verify that smokers will tolerate multiple administrations across separate days of similar cued threat tasks.

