Analysis of Treatment Outcome (AIMS 3, 4.1, 4.2): Number of cigarettes smoked (17,18), point prevalence abstinence and continuous abstinence (as defined by the SRNT Workgroup on Biochemical Confirmation (149)) will be analyzed in Generalized Linear Models with time (1 week vs. 2 weeks) as a within subject factor. Startle potentiation measures from the cued threat task will be included as quantitative regressors to test if our laboratory stress neuroadaptation biomarkers predict treatment outcome measures (Aim 3). As above, treatment condition can be included as a moderating between subject factor to test if the relationships between startle potentiation and treatment outcome differ generally when withdrawal symptoms. Finally, mediation analyses can be conducted to determine if NRT alters startle potentiation measures at one-week post quit (AIM 4.1) and the startle potentiation measures mediate NRT effects on smoking outcome measures (AIM 4.2).

C4.3: Sample Size Justification. The primary analyses of startle potentiation will be accomplished within the General Linear Model (GLM). The analyses of smokers test for a two way interaction between Deprivation Status and Threat Uncertainty. Cohen (150) defines 0.15 for the squared multiple partial correlation as a medium effect size for GLM analyses. To be conservative, we powered our experiments to provide 90% power to detect a somewhat smaller (0.10) effect size. N=142 will provide 90% power to detect a squared multiple partial correlation of 0.10 for the interaction in a model that contains the two main effects and interaction based on formula provided by Cohen. We then increased this sample size to the round 150 within each Treatment Group to provide flexibility to counterbalance all relevant additional task factors. This yields N=300 across the two Treatment Groups. Given that the multilevel models that will be used to test questions about the EMA data are essentially GLMs fit at two separate levels of analysis (occasion and person levels), N=150 within each Treatment Group will provide comparable high power to test person-level predictors of both occasion-level intercepts (e.g., overall smoking, levels of negative affect) and stressor coefficients (e.g., stress-instigated smoking or negative affect).

DATA AND RECORD KEEPING

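### Half the sample has no pre-quit startle score as Aims 4.2 and 4.3 require, and the Aim 2, 3 and 4.3 models name neither the session nor Deprivation Status

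*Combined protocol and SAP*

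**What the plan says.** **Schedule.** Section C2.2 randomises participants to a deprivation condition; those in the deprived condition are "instructed to abstain from all nicotine containing products for 24 hours prior to their nicotine deprived session". Section C2.3 gives two task sessions, the second at 2 weeks post-quit, and states that "The deprived group completes their first experimental session the day after the start of their quit attempt". Section C3 agrees: "Participants in the non-deprived group will complete the task once pre-quit; in the deprived group, immediately post-quit".

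**Aims.** Aim 4.2 says that the treatment effect "will be mediated by change in startle potentiation measures from pre-quit to post-quit". Aim 4.3 says that combination NRT "will attenuate the predictive strength of pre-quit startle potentiation measures".

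**Models.** The EMA analysis (Aims 2 and 4.3) enters startle as a person-level variable to "predict individual differences in overall levels of negative affect, urge, or smoking over the 3-weeks of EMA controlling for stressor exposure". The treatment outcome analysis says, for Aim 3, that "Startle potentiation measures from the cued threat task will be included as quantitative regressors". Neither names a session or a Deprivation Status term. That factor appears only in the Aim 1 analysis and in the sample size section C4.3. The Aim 1 analysis treats it as within-subject over two pre-quit sessions, and C2.4.1 likewise refers to a deprived session before quitting.

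**The concern.** Two things follow if the plan is applied as written.

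- **Undefined quantities.** The deprived group's first session is already post-quit. The Aim 4.3 predictor and the starting point of the Aim 4.2 change are missing for that group unless the analyst substitutes something. The obvious substitute is the first session, whatever its state.
- **A pooled regressor.** That substitute mixes deprived and non-deprived scores. Aim 1.1 predicts that deprivation raises startle under uncertain threat, so the regressor would carry a randomised state shift on top of the person-level trait it is meant to index. The slope is then diluted. If the deprivation condition also moves smoking or affect, the slope is biased as well.

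One possible route to such a shift is medication timing. Section C2.3 says: "On completion of the task, participants receive brief cessation counseling, and combo NRT or placebo NRT according to their randomized treatment condition". Read with the session schedule, that falls on different sides of the quit date in the two groups.

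**Working it through.** **1. The plan's own figure.** C4.3 gives N=142 for 90% power at an effect of 0.10, described as a squared partial correlation for the Deprivation Status by Threat Uncertainty interaction. Alpha is not stated; 0.05 is assumed throughout. Using f²=0.10 with 3 numerator df, the noncentrality needed is 14.17, and 14.17/0.10 = 141.7, so 142. Read literally (partial R²=0.10, 1 df), an exact F test needs only N=97. The figure is reproduced, but not on the stated definition, so 0.10 is a loose guide to the size of the state shift.

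**2. State share of the regressor.** Assume a 50:50 split and a mean shift of d within-group SDs. The share of pooled startle variance due to state is S = (d²/4)/(1+d²/4), and the unadjusted slope is (1−S) times the within-group slope.

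- Between-person reading of 0.10: d = 2√(0.10/0.90) = 0.667, so S = 10.0%.
- Within-subject reading (the Aim 1 analysis text): dz = √(0.10/0.90) = 0.333 and d = dz√(2(1−ρ)). For an assumed session correlation ρ=0.3, d=0.394 and S=3.7%; for ρ=0.7, d=0.258 and S=1.6%.
- Certain-threat startle: section A3 reports no deprivation effect, so S is near zero.

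**3. Power.** This uses a 1-df F test with noncentrality N·R²/(1−R²). R² is the assumed within-group startle-outcome value, and R²(1−S) applies when Deprivation Status is omitted. A single normal outcome is assumed. Entries are power with, then without, the term.

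| State share S | N=300, R²=0.05 | N=300, R²=0.025 | N=150, R²=0.05 | N=150, R²=0.025 |
|---|---|---|---|---|
| 10.0% | 0.977, 0.963 | 0.789, 0.745 | 0.797, 0.752 | 0.495, 0.455 |
| 3.7% | 0.977, 0.973 | 0.789, 0.774 | 0.797, 0.781 | 0.495, 0.480 |
| 1.6% | 0.977, 0.975 | 0.789, 0.783 | 0.797, 0.790 | 0.495, 0.489 |

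**4. Bias.** Suppose startle has no true effect but outcomes differ by c SD between deprivation groups. The spurious correlation is r = √S·(c/2)/√(1+c²/4). For c=0.2 and N=300, r is 0.013, 0.019 and 0.032 at S = 1.6%, 3.7% and 10%. Type I error is about 0.055, 0.063 and 0.084. With Deprivation Status in the model it is 0.05 (0.051 in simulation). The value of c is an assumption; the documents give none.

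**5. Aim 4.2 mediator.** On the between-person reading, state is (d²/4)/(2(1−ρ)+d²/4) of raw-change variance: 7.4%, 10.0% and 15.6% at ρ = 0.3, 0.5 and 0.7. On the within-subject reading d²/4 = dz²(1−ρ)/2, so the share is 0.0278/1.0278 = 2.7% at any ρ. At d=0.667 the residual variance is 1.511, 1.111 and 0.711 for raw change. It is 1−ρ² = 0.910, 0.750 and 0.510 for post-quit startle adjusted for session-1 startle and Deprivation Status. That is 28-40% lower. Deprivation Status contributes only 1%, 3% and 9% beyond session-1 startle.

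**6. Unequal slopes.** Suppose startle predicts only when measured deprived, with R²=0.10 there, and d=0.667. The pooled R² is (0.10/4)/(1+0.111) = 0.0225, with power 0.455 at N=150 and 0.745 at N=300. Adding only the main effect raises R² to 0.10/4 = 0.025, with power about 0.495 and 0.789. It does not recover the slope that exists in the deprived group.

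**The case against.** **The plan does not exclude the term.** A reader might infer that it does. The documents do not support that: the statistical section calls its models exemplars and says supplemental analyses are left out, the covariate and moderator lists are open, and A5 and C2.5 speak of using deprived and non-deprived startle. This stands. However, those passages presume that both states are measured in each person, which the schedule does not provide, and no model carries the intention through. That session 1 is the intended predictor for Aims 2 and 3 is itself an inference, made because session 2 falls at the end of the outcome period.

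**The 10% figure is borrowed.** A reader might take 10% attenuation as the expected loss. It is only one reading of an effect the trial was powered to detect, for an interaction rather than for the regressor. The within-subject reading gives 2-4%, and certain-threat startle about zero. This stands, and so both readings are shown.

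**The outcome models differ.** Aim 3 uses counts and binary abstinence, and Aim 2 is multilevel. The figures are indicative and belong to no planned model.

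**Bias is hypothetical.** A reader might infer that the startle slopes are biased. Deprivation is randomised, so omitting it causes bias only if it also shifts outcomes. Medication timing is a possible route rather than an established one: C2.4 also places a counselling contact 24 hours into quitting for participants in general, so the timing of dispensing is not clear.

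**A covariate does not remove every problem.** This also stands. It corrects neither unequal slopes nor the selection in C2.3, where only the deprived session carries an abstinence requirement and two failures end participation.

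**Conclusion.** The pre-quit definitions in Aims 4.2 and 4.3 are wrong as written for the deprived group, and the two-pre-quit-session wording in the Aim 1 analysis and C2.4.1 does not match C2.2, C2.3 and C3. That is a contradiction within the document and depends on no assumption.

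The missing session and Deprivation Status term in the Aim 2, 3 and 4.3 models is a gap that can be closed almost free, for a modest gain. Under uncertain threat, slope attenuation is about 2-4% or about 10%, depending on how 0.10 is read. The power loss runs from 0.2 to about 4.5 points over the cases tabulated. If deprivation assignment shifted outcomes by an assumed 0.2 SD, type I error at N=300 would be about 0.055-0.084 instead of 0.05. These figures rest on a 50:50 split, alpha 0.05, equal slopes where power is quoted, session correlations of 0.3-0.7 for the within-subject reading, and a single normal outcome.

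**What to change.** - **Definitions.** Replace the pre-quit wording in Aims 4.2 and 4.3 by session-1 startle, and name session-1 startle as the predictor for Aims 2 and 3. Reconcile the Aim 1 analysis text, C2.4.1 and the within-subject wording in C2.3 with the schedule. State whether the deprivation and treatment assignments are independent.
- **Aims 2, 3 and 4.3.** Add Deprivation Status, as randomised, as a main effect. In the coupling models also let it predict the stressor slope. Report the Deprivation Status by startle interaction and the slope within each deprivation group as prespecified secondary results, because the main effect does not address unequal slopes.
- **Aim 4.2.** Use post-quit startle adjusted for session-1 startle and Deprivation Status in both the treatment-to-mediator and the mediator-to-smoking models, in place of raw change. The same adjustment is an optional precision gain for Aim 4.1.

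**Cost.** One degree of freedom per model, two in the coupling models, plus wording; no new data.

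**Limits.** The interaction test is weak. If the non-deprived slope is half the deprived slope (deprived R²=0.10, slopes 0.316 and 0.158), the noncentrality at N=300 is 300×0.079²/0.90 = 2.1 and power is about 0.30. The change does not undo the one-sided discontinuation for failed abstinence. Nor does it make session-1 startle prospective for the pre-quit EMA week in the deprived group.
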